### 7.1.2. Primary Effectiveness Endpoint

The primary effectiveness endpoint is a composite of all-cause mortality, disabling stroke, or moderate or greater paravalvular aortic regurgitation (based on core lab assessment) at 1 year. The primary analysis set for the primary effectiveness endpoint is the implanted analysis set.

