- d: Neurological physical examination must be performed by a neurologist, neurology fellow, neurology physician assistant, or neurology nurse practitioner. NIHSS and mRS must be performed by a neurology professional or certified personnel (external certification for NIHSS; internal or external certification for mRS). The assessors should be independent (not involved with the care of study subjects). For subjects diagnosed with a neurological event (e.g., stroke, transient ischemic attack), a neurological physical exam, mRS, and NIHSS must be performed after the event; mRS must also be administered at 90±14 days post-neurological event. If a subject who has not received a study device (investigational or control) experiences a neurological event within the first 1 year after the index procedure, mRS must be performed on that subject after the event and at 90±14 days post-neurological event and the results must be reported to the Sponsor.
- e: All screening and post-procedure 12-lead ECGs must be performed according to the ECG Core Laboratory guidelines (see study Manual of Operations). Heart

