### 11.10.3.12-Month (365±30 Days) Follow-up

All implanted subjects must be evaluated at 12 months after the index procedure. During the 12-month follow-up, the following assessments must be completed. The REPRISE III eCRFs identify the specific data points to be collected.

- Physical examination including weight and height
- NYHA classification
- Modified Rankin Scale score, which must be performed by a neurology professional or certified personnel (external or internal certification); assessors should be independent (not involved with the care of study subjects).
- Neurological physical examination, which must be performed by a neurologist, neurology fellow, neurology physician assistant, or neurology nurse practitioner (see Table 11.1-1); assessors should be independent (not involved with the care of study subjects).
- NIHSS, which must be performed by a neurology professional or certified personnel (external certification); assessors should be independent (not involved with the care of study subjects).
- Gait speed to walk 5 meters
- Rotational x-ray angiography performed on subjects who received the Lotus Valve to assess for structural valve frame integrity per the Imaging Core Laboratory procedure guidelines (see study Manual of Operations). It must be forwarded to the Core Laboratory for analysis.
- 12-lead ECG per the Core Laboratory Guidelines (see study Manual of Operations) and must be forwarded for analysis
- Current antiplatelet and anticoagulant (if applicable) medications
- TTE, including assessment of effective orifice area, peak systolic and mean aortic valve gradient pressure, aortic regurgitation assessment, mitral regurgitation, LVEF, left ventricular end-diastolic and end-systolic diameter, TR jet velocity and LA volume, per the Echocardiography Core Laboratory procedure guidelines (see study Manual of Operations). It must be forwarded to the Core Laboratory for independent analysis.  
**Note:** TTE must be done for all subjects who have a valve implanted in the aortic position during the index procedure. Subjects who do not receive a transcatheter valve during the index procedure are not required to have follow-up TTE.
- Complete adverse event (AE, SAE, SADE, UADE/USADE, ADE and CEC events) and device deficiencies assessment (with associated treatment)
- Quality of Life Surveys: Kansas City Cardiomyopathy and SF-12 Quality of Life Questionnaires

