### 12.2.2. Control of Systematic Error/Bias

All subjects who have met the inclusion/exclusion criteria, received a positive recommendation from the CRC, and signed the Informed Consent Form will be eligible for

enrollment in the study. The center heart team's assessment of TTE measurements before device placement will contribute to the determination of subject eligibility for the study.

To control for inter-observer variability, data from independent core laboratories (see Section 13.3) will be used for analysis. These include an echocardiography core lab, a CT and rotational X-ray angiography core laboratory to assess all CT and rotational X-ray data using standard techniques, and an electrocardiography core laboratory to independently analyze protocol-required 12-lead ECGs performed for each subject.

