#### **22.1.1. Clinical Events Committee**

A CEC will be used in this study. A CEC is an independent group of individuals with pertinent expertise, including cardiovascular interventional therapy, cardiovascular surgery, and neurology, which reviews and adjudicates important endpoints and relevant adverse events reported by study investigators. The CEC will review a safety event dossier, which may include copies of subject source documents provided by study sites, and adjudicate study endpoint related clinical events. The responsibilities, qualifications, membership, and committee procedures of the CEC are outlined in the CEC charter.

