STROKE 	
Stroke is defined as an acute episode of focal or global neurological dysfunction caused by brain, spinal cord, or retinal vascular injury as a result of hemorrhage or infarction
 
Stroke Classification
 
 
• Ischemic Stroke is defined as an acute episode of focal cerebral, spinal, or retinal dysfunction caused by an infarction of central nervous system tissue.
 
• Hemorrhagic Stroke is defined as an acute episode of focal or global cerebral or spinal dysfunction caused by an intraparenchymal, intraventricular, or subarachnoid hemorrhage
 
 
Note 1: The CEC will adjudicate ischemic versus hemorrhagic stroke. Note 2: A stroke may be classified as undetermined if there is insufficient information to allow categorization as ischemic or hemorrhagic
 
Stroke Diagnostic Criteria
 
 
• Rapid onset of a focal or global neurological deficit with at least one of the following: change in level of consciousness, hemiplegia, hemiparesis, numbness or sensory loss affecting one side of the body, dysphasia or aphasia, hemianopia, amaurosis fugax, or other neurological signs or symptoms consistent with stroke
 
• Duration of a focal or global neurological deficit <math>\geq 24</math> h; OR <math>< 24</math> h, if available neuroimaging documents a new hemorrhage or infarct; OR the neurological deficit results in death
 
• No other readily identifiable nonstroke cause for the clinical presentation (e.g., brain tumor, trauma, infection, hypoglycemia, peripheral lesion, pharmacological influences), to be determined by or in conjunction with designated neurologist
 
• Confirmation of the diagnosis by at least one of the following. 
 
○ Neurology or neurosurgical specialist
 
○ Neuroimaging procedure (MRI or CT scan), but stroke may be diagnosed on clinical grounds alone
 
 
 
 
Note 3: Subjects with non-focal global encephalopathy will not be reported as a stroke without unequivocal evidence based upon neuroimaging studies (CT scan or brain MRI).
 
Stroke Definitions
 
Diagnosis as above, preferably with positive neuroimaging study
 
 
• Non-disabling: Modified Rankin Scale (mRS) score <math>< 2</math> at 90 days OR one that does not result in an increase of at least one mRS category from an individual's pre-stroke baseline
 
• Disabling: Modified Rankin Scale score <math>\geq 2</math> at 90 days AND an increase of at least one mRS category from an individual's pre-stroke baseline
 
 
Note 4: Modified Rankin Scale assessments should be made by a neurology professional or by qualified individuals according to a certification process. Note 5: Assessment of the mRS score should occur at all scheduled visits in a study; mRS also should be performed after a stroke and at 90 days after the onset of any stroke.

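### The assessors who score the 90-day Rankin scale, which separates disabling from non-disabling stroke, should be independent of care, but nothing in the protocol keeps the valve from them

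*Combined protocol and SAP*

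**What the plan says.** The primary effectiveness endpoint (Section 7.1.2) is the "composite of all-cause mortality, disabling stroke, or moderate or greater paravalvular aortic regurgitation (based on core lab assessment) at 1 year". Table 26.2-1 calls a stroke disabling when the mRS is 2 or more "at 90 days AND an increase of at least one mRS category from an individual"; the reference is the person's state before the stroke.

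On who scores it, the same table says: "Modified Rankin Scale assessments should be made by a neurology professional or by qualified individuals according to a certification process". Footnote d to Table 11.1-1 makes certification or neurology training mandatory and then adds: "The assessors should be independent (not involved with the care of study subjects". The baseline (11.5), discharge (11.9), 30-day, 6-month, 12-month and annual (11.10.1 to 11.10.4) sections repeat this; the 12-month text reads "assessors should be independent (not involved with the care of study subjects". The verb is should throughout, so independence itself is recommended, not required.

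On bias control, Section 12.2.2 covers eligibility and committee review of candidates, and then states: "To control for inter-observer variability, data from independent core laboratories" will be used. The laboratories it names are echocardiography, CT and rotational X-ray, and ECG.

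On adjudication, Section 22.1.1 says "A CEC is an independent group of individuals with pertinent expertise", neurology among them. It also says: "The CEC will review a safety event dossier, which may include copies of subject source documents provided by study sites". Sections 7.2 and 21.1 list disabling and non-disabling stroke among the events that the CEC adjudicates. Its procedures are left to a charter.

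**The concern.** Death needs no severity judgement, and paravalvular regurgitation is read by a core laboratory. Disabling stroke is the component that turns on a graded clinical score given at the site: a difference of one mRS category can decide whether a stroke counts. The protocol describes no blinding to treatment for anyone. Operators plainly know the valve, but a separate mRS assessor need not, and the protocol already wants that assessor to come from outside the care team. Being outside the care team is not the same as being unaware of the device.

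If knowing the valve led assessors to score one arm's strokes more leniently, the composite would shift in that arm. Lenient scoring of Lotus strokes makes a false finding of non-inferiority more likely; strict scoring costs power. The superiority test of the same composite (Section 12.1.2.1.2) would carry the same shift.

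Ordinary trial records can reveal the arm. Section 11.7 has the device type or model recorded at the procedure, and rotational X-ray at 12 months is required only for recipients of the Lotus valve.

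**Working it through.** **Where blinding could be stated**

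| Place | What it asks | Valve kept from the person? |
|---|---|---|
| Footnote d; 11.5, 11.9, 11.10 | independence from care; certification or neurology training | not stated |
| Table 26.2-1, stroke note 4 | certification or neurology training | not stated |
| 12.2.2 | eligibility review; core laboratories | not stated; none of these laboratories scores stroke disability |
| 22.1.1 | independent committee, dossier from sites | not stated; charter not supplied |
| 7.2, 11.10.1, 11.10.3 | CT valve findings withheld from local investigators | concerns CT findings in a Lotus-only cohort, not treatment arm |

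**The plan's own figure**

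Inputs (Section 12.1.2.2.1): 32% in both arms, margin 0.095, one-sided 0.025, 2:1 allocation, 80% power, 819 evaluable, 10% attrition. For the Farrington-Manning test,

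P(reject) = Φ{[0.095 − (pT − pC) − 1.96·s0] / s1},

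where s0 is the standard error at the restricted maximum-likelihood rates (difference fixed at the margin) and s1 is the standard error at the true rates. With 546 Lotus and 273 CoreValve subjects and pT = pC = 0.32, the restricted rates are 0.3554 and 0.2604, s0 = 0.03354 and s1 = 0.03458. Then (0.095 − 0.0657)/0.03458 = 0.846, and power is 80.1%. The 819 reproduces. 819/0.9 = 910, against 912 planned. The concern disputes neither number.

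**Illustration of a one-sided scoring shift**

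Document input: 9 of 249 subjects (3.6%) had a disabling stroke by 1 year in the REPRISE II full cohort (Table 4.1-4). Assumptions: true difference equal to the margin (pC = 0.32, pT = 0.415); a fraction f of Lotus disabling strokes scored non-disabling; CoreValve unaffected; none of those patients also counted through death or regurgitation. The observed Lotus rate becomes 0.415 − 0.036f.

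| f | Shift (points) | Lotus rate | s0 | s1 | z | Type I error |
|---|---|---|---|---|---|---|
| 0 | 0 | 41.50% | 0.03524 | 0.03524 | −1.960 | 2.5% |
| 10% | 0.36 | 41.14% | 0.03518 | 0.03522 | −1.856 | 3.2% |
| 25% | 0.90 | 40.60% | 0.03510 | 0.03520 | −1.699 | 4.5% |
| 50% | 1.80 | 39.70% | 0.03496 | 0.03515 | −1.437 | 7.5% |

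For f = 25%: 0.095 − (0.406 − 0.320) = 0.009; 0.009 − 1.96 × 0.0351 = −0.0598; −0.0598/0.0352 = −1.699. As a share of the margin, the three shifts are 0.36/9.5 = 4%, 0.90/9.5 = 9% and 1.80/9.5 = 19%.

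At the low end, with the 1.7% disabling stroke rate of the REPRISE II main cohort at 30 days (Table 4.1-2), the type I error is about 2.8%, 3.3% and 4.3%.

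In the other direction, with equal true rates of 32%, an upward shift of 0.9 points in the Lotus arm gives s0 = 0.03373 and s1 = 0.03466. Then (0.095 − 0.009 − 1.96 × 0.03373)/0.03466 = 0.574, and power falls from 80% to 72%.

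**The case against.** The protocol is not without safeguards. Assessors are asked to be outside the subject's care and must be certified or neurology-trained. A neurological examination and NIHSS are required after any event, so the mRS does not reach the CEC alone. The CEC, with neurology expertise, makes the formal classification. This stands, and it limits the likely bias. It does not close the gap: the 90-day score still comes from the site, and no supplied text keeps the valve from the assessor or the committee.

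Four stronger readings are tempting and are not supported.

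- *Assessors are told the valve, or the CEC sees it.* The text is silent; it neither discloses nor withholds. The CEC charter and the Manual of Operations are cited but not supplied, and either could contain a blinding rule.
- *A quarter of all strokes could cross the line, moving the composite by 0.25 × 8.4 = 2.1 points, or 22% of the margin.* REPRISE II had 21 strokes in 249 subjects, 9 disabling and 12 not. A quarter of 21 is 5.25 patients. Moving them all one way means rescoring 5.25/9 = 58% of disabling strokes. A quarter crossing from each side nets 3 − 2.25 = 0.75 patients, about 0.3 points. The arithmetic also ignores stroke patients who die within the year and count regardless.
- *The CT substudy shows that the sponsor blinds where it cares to.* That rule withholds imaging findings in a cohort where everyone receives Lotus. It says nothing about intent on treatment arm.
- *Bleeding, vascular and death dossiers need redaction too.* No bias has been shown for those events here. At the planned 40% safety event rate, about 0.40 × 912 = 365 subjects would have an event, so the work would not be small.

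**Conclusion.** The point holds as a gap in the supplied text. The score that decides whether a stroke is disabling, and so whether it counts as one in the primary effectiveness endpoint, is given by assessors who should be independent but from whom nothing in the protocol withholds the valve. Section 12.2.2 does not make up for this, and Section 22.1.1 does not say that it does.

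The size is modest. For 10% to 50% one-way rescoring of Lotus disabling strokes, type I error at the margin rises from 2.5% to between about 3.2% and 7.5% at a 3.6% disabling stroke rate, or between 2.8% and 4.3% at 1.7%. The rescoring fractions are assumptions, the stroke rates come from a Lotus-only study and say nothing about a difference between arms, and the calculation assumes no overlap with death or regurgitation. Overlap would shrink the effect. The documents give no evidence that such bias occurred.

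This is a worthwhile, inexpensive improvement, not a defect that undermines the endpoint. A suitable CEC charter would settle the committee part but not the assessor part.

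**What to change.** In footnote d of Table 11.1-1 and in Sections 11.5, 11.9 and 11.10, state: *Assessors must be independent of care and must not be told, or look up, the assigned or implanted valve; the form records whether the assessor was unblinded.*

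In Section 22.1.1, state that device identity is redacted from stroke dossiers where feasible, or cross-refer to the CEC charter if it already says so.

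The cost is protocol wording, one form field and redaction confined to stroke dossiers. No assessor, visit or subject is added. Some assessors will still learn the valve; the form field makes this visible and allows a sensitivity analysis restricted to blinded scores.

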**Table 11.1-1: Study Event Schedule**

Assessment	Screening a	Baseline	Procedure	Within 1 Day Post-procedure	Prior to Discharge or 7 Days Post-Procedure	30 Days b (±7 Days) Office Visit	6 Months b (±30 Days) Office Visit	12 Months b (±30 Days) Office Visit	24–60 Months b [Annual] (±45 Days) Office Visit
------------	------------------------	----------	-----------	-----------------------------	---	---	---	--	--

rhythm strip should be obtained after BAV and before study valve insertion (12-lead ECG is not required during the procedure).

- f: Laboratory tests at baseline include CBC with platelets, albumin, serum creatinine, and cardiac enzymes. Cardiac enzymes (CK is required, CK-MB or troponin if CK is elevated) must be collected twice at intervals per standard of care within 6-24 hours post-procedure. Acute kidney injury (AKI) should be assessed through discharge/7 days based on the AKIN system.
- g: Consists of STS score, euroSCORE II (2011), and heart team assessment including an in-person evaluation by a center cardiac surgeon that must be confirmed by the CRC (which must include an experienced cardiac surgeon). In the United States, the Centers for Medicare and Medicaid Services require independent evaluations by 2 cardiac surgeons for reimbursement.
- h: Frailty, disability, and comorbidity risk assessments must be captured at screening: height, weight, cognitive function (Mini-Cognitive Assessment for Dementia), strength and balance (use of wheelchair, gait speed to walk 5 meters, number of falls in the past 6 months, maximal grip strength), and activities of daily living (Katz Index); at 1 year, gait speed to walk 5 meters must be assessed again.
- i: Transthoracic echocardiogram (TTE) is required for all subjects who have a valve implanted in the aortic position. This includes assessment of EOA, peak and mean aortic valve pressure gradients, aortic regurgitation assessment, and LVEF. Screening TTE must be performed within 60 days prior to CRC review. At least 1 echocardiogram must be obtained before discharge or 7 days (whichever comes first); if multiple echocardiographic studies are performed prior to discharge and within 7 days of the procedure, the latest study performed will be used for analysis. All TTEs must be performed according to the Echocardiography Core Laboratory procedure guidelines (see study Manual of Operations). If a subject does not receive an implanted valve, then no follow-up TTE is required.  
**Note:** In cases of low flow low gradient aortic stenosis, dobutamine can be used to assess the grade of aortic stenosis; the subject may be enrolled if echocardiographic criteria are met with this augmentation. In cases where a subject who has met the echocardiographic criteria for enrollment receives BAV prior to the index procedure and subsequently no longer meets the REPRISE III aortic valve pressure gradient or EOA criteria, the subject may still be enrolled based on the pre-BAV echocardiographic data. In such cases, the most recent echocardiogram done prior to the index procedure (even if after BAV) must be submitted to the Echocardiography Core Laboratory to be included in the baseline data.
- j: TEE is recommended but not required during the implant procedure.
- k: A coronary angiogram must be performed within 365 days prior to CRC review. If there is concern regarding the current extent of coronary artery disease or aortic stenosis, the CRC may recommend a repeat study closer to the time of enrollment.
- l: A CT angiogram of the aortic complex must be performed within 180 days prior to CRC review (and should be performed within 90 days if possible) to evaluate the aortic valve anatomy and aortic root dimensions for device sizing. CT angiogram must be performed according to the CT/X-ray Core Laboratory procedure guidelines (see study Manual of Operations). It must be sent to the Core Laboratory for detailed measurements and analyses in advance of the CRC meeting where results will be reviewed to confirm subject's eligibility.
- m: An assessment of the iliofemoral system must be performed within 180 days prior to CRC review (and should be performed within 90 days if possible). A CT angiogram of the iliofemoral system should be performed for complete visualization of the iliac and femoral arteries to assess for dimensions, tortuosity, and calcification. The CT angiogram should be performed per the procedure guidelines (see study Manual of Operations) and sent to the CT Core Laboratory with the screening CT angiogram of the aortic structure. An iliofemoral invasive angiogram may be substituted for the iliofemoral CT angiogram.
- n: Annual imaging using rotational x-ray to assess for structural valve frame integrity must be performed on subjects who receive the Lotus Valve. Please refer to the

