### 11.5. *Baseline Assessments*

The following assessments must be completed within 30 days prior to the index procedure, unless otherwise specified below. The REPRISE III electronic eCRFs identify the specific data points to be collected.

- Confirmation of eligibility criteria
- Neurological physical examination, which must be performed by a neurologist, neurology fellow, neurology physician assistant, or neurology nurse practitioner (see Table 11.1-1); assessors should be independent (not involved with the care of study subjects).
- NIH Stroke Scale (NIHSS), which must be performed by a neurology professional or certified personnel (external certification); assessors should be independent (not involved with the care of study subjects)
- Modified Rankin Scale score, which must be performed by a neurology professional or certified personnel (external or internal certification); assessors should be independent (not involved with the care of study subjects)
- Laboratory tests
  - Complete blood count (CBC) with platelets
  - Albumin
  - Serum creatinine
  - Cardiac enzymes (CK is required, CKMB or troponin if CK is elevated)
- Quality Of Life (QOL) Surveys: Kansas City Cardiomyopathy and SF-12 QOL Questionnaires must be administered to the subject within 30 days prior to the procedure.

**Note:** In cases where a subject who has met the echocardiographic criteria for enrollment receives BAV prior to the index procedure and subsequently no longer meets the REPRISE III aortic valve pressure gradient or EOA criteria, the subject may still be enrolled based on the pre-BAV echocardiographic data. In such cases, the most recent echocardiogram done prior to the index procedure (even if after BAV) must be submitted to the Echocardiography Core Laboratory to be included in the baseline data.

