### 11.8. *Post-Procedure*

The following are to be performed post-procedure.

- Per society guidelines, antiplatelet therapy with aspirin and a thienopyridine is recommended to reduce the risk of thrombotic or thromboembolic complications if there are no contraindications to these medications. Subjects must be treated with aspirin and clopidogrel for at least 1 month following valve implantation. Extended dual antiplatelet therapy may be administered per physician choice.
  - After the valve implant procedure, aspirin (recommended dose of  $\geq 75$  mg daily) must be given for at least 1 month. It is recommended that daily aspirin be given indefinitely thereafter as per local standard of care. Aspirin dose may be adjusted to the closest approximation based on local tablet formulation availability.

- After the valve implant procedure, clopidogrel (recommended dose of 75 mg daily) is required for at least 1 month.  
*Note:* An alternative P2Y12 inhibitor (e.g., ticlopidine) may be prescribed if subject is allergic to or intolerant of clopidogrel.
- If a subject requires chronic anticoagulation, either clopidogrel or aspirin is required after the implant procedure in addition to the anticoagulant therapy (but both aspirin and clopidogrel are not required). The subject must be treated with warfarin (other anticoagulants are not permitted in the first month) and either clopidogrel (other P2Y12 inhibitors are not permitted in combination with warfarin) or aspirin for at least 1 month. After 1 month, subjects requiring chronic anticoagulation may be switched from warfarin to a new oral anticoagulant (NOAC) at the discretion of the treating physician. The subject should not receive a P2Y12 inhibitor in combination with a NOAC but may be treated with a NOAC plus aspirin.
- Prophylactic antibiotic regimen should be completed as per local practice.
- Additional medications may be used at the investigator's discretion.
- It is recommended that the subject's heart rhythm be monitored using telemetry for at least 48 hours after the index procedure.
- 12-lead ECG must be completed within 24 hours post-procedure per the ECG Core Laboratory guidelines (see study Manual of Operations) and must be forwarded to the Core Laboratory for analysis.
- Cardiac enzymes (CK is required, CK-MB or troponin if CK is elevated) must be collected twice at intervals per standard of care within 6-24 hours post-procedure.

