Anticoagulation medication (e.g., heparin) will be administered during the procedure to reduce the risk of embolism and stroke. Additionally, post-procedure anti-platelet therapy is recommended to minimize any risk of thrombus formation, stroke, or transient ischemic attack. Neurological assessments will be performed at each required follow-up visit to identify any change in the neurological status of the subjects as recommended by VARC.

Cardiac enzyme measurements as well as ECGs post-procedure will be performed to detect periprocedural MI.

Subjects will be carefully monitored during the procedure, hospitalization, and throughout the follow-up period. Serial echocardiograms and electrocardiograms will be used to evaluate valve and general cardiac function. Any abnormal rhythm will be assessed and, if needed, the implantation of a permanent pacemaker will be performed. Annual imaging will also be performed to assess for structural valve frame integrity.

Subjects who are converted to standard surgical aortic valve replacement will be carefully monitored in a method appropriate for their surgical procedure.

Data will be monitored as they are submitted to BSC. Qualified employees of BSC, or a designee under contract, will conduct monitoring visits at the initiation of the study and at interim intervals described in the monitoring plan throughout the course of the study to evaluate protocol compliance and determine if there are any issues that could affect the safety or welfare of any subject in the study.

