MYOCARDIAL INFARCTION (MI)	
Periprocedural MI (<math>\leq 72</math> hours after the index procedure)
 
 
• New ischemic symptoms (e.g., chest pain or shortness of breath) or new
 

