**Table 26.2-1: Definitions**

Term	Definition								
	
ischemic signs (e.g., ventricular arrhythmias, new or worsening heart failure, new ST-segment changes, hemodynamic instability, new pathological Q waves in at least two contiguous leads, or imaging evidence of new loss of viable myocardium or new wall motion abnormality)
 
-AND-
 
 
• Elevated cardiac biomarkers (preferably CK-MB) within 72 h after the index procedure, consisting of at least one sample post-procedure with a peak value exceeding 15× upper reference limit (troponin) or 5× for CK-MB. If cardiac biomarkers are increased at baseline (>99th percentile), a further increase of at least 50% post-procedure is required AND the peak value must exceed the previously stated limit.
 
 
Spontaneous MI (>72 hours after the index procedure) Any one of the following criteria applies.
 
 
• Detection of rise and/or fall of cardiac biomarkers (preferably troponin) with at least one value above the 99th percentile URL, together with evidence of myocardial ischemia with at least one of the following 
 
○ Symptoms of ischemia
 
○ ECG changes indicative of new ischemia [new ST-T changes or new LBBB]
 
○ New pathological Q waves in at least two contiguous leads
 
○ Imaging evidence of new loss of viable myocardium or new wall motion abnormality
 
 
 
• Sudden, unexpected cardiac death, involving cardiac arrest, often with symptoms suggestive of myocardial ischemia, and accompanied by presumably new ST-segment elevation, or new LBBB, and/or evidence of fresh thrombus by coronary angiography and/ or at autopsy, but death occurring before blood samples could be obtained, or at a time before the appearance of cardiac biomarkers in the blood.
 
• Pathological findings of an acute myocardial infarction.
 
								
NEUROLOGICAL EVENT	Any central, new neurological deficit, whether temporary or permanent and whether focal or global, that occurs after the subject emerges from anesthesia								

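### When total CK is normal but new ischemic symptoms or signs appear, the required blood tests cannot settle the biomarker criterion for periprocedural MI

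*Combined protocol and SAP*

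**What the plan says.** **Collection.** Footnote f of Table 11.1-1 and Section 11.8 cover the two draws between 6 and 24 hours after the procedure. Footnote f reads "Cardiac enzymes (CK is required, CK-MB or troponin if CK is elevated) must be collected twice", and Section 11.8 reads "Cardiac enzymes (CK is required, CK-MB or troponin if CK is elevated) must be collected twice at intervals per standard of care". Section 11.5 applies the same condition at baseline: "Cardiac enzymes (CK is required, CKMB or troponin if CK is elevated". None of the three places gives a cut-off for an elevated CK.

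**Definition.** Table 26.2-1 builds periprocedural MI from two elements joined by AND. The first begins "New ischemic symptoms (e.g., chest pain or shortness of breath) or new" and goes on to list ischemic signs. The second is "Elevated cardiac biomarkers (preferably CK-MB) within 72 h after the index procedure", "consisting of at least one sample post-procedure with a peak value exceeding" 15 times the upper reference limit for troponin or 5 times for CK-MB. If the marker was already above the 99th percentile at baseline, "a further increase of at least 50% post-procedure is required", and the peak must still pass the limit. Total CK has no threshold in this definition.

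**Purpose.** Section 19.2 says: "Cardiac enzyme measurements as well as ECGs post-procedure will be performed to detect periprocedural MI". Footnote t of Table 11.1-1, Section 11.10 and Section 21.1 all point to the event definitions for the data that adjudication needs.

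**Status.** Section 7.2 lists periprocedural MI among the safety endpoints adjudicated by the Clinical Events Committee (CEC). Section 12.1.5 presents differences between arms with 95% confidence intervals, but plans no inference on these additional measurements.

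**The concern.** The endpoint turns on CK-MB or troponin. The schedule makes both conditional on a third marker that plays no part in the endpoint. A subject can have chest pain or new ST changes after the procedure, complete every required test, and still have nothing to compare with either threshold. Such a subject could be left unclassified or be counted, without any stated rule, as having no MI.

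Whether a troponin is run in these subjects then depends on local discretion. Site staff can know which valve was implanted, so ascertainment could differ by arm, although nothing in the documents shows that it will. A second weakness is that no text requires the same marker before and after the procedure, although the 50% rule compares the two.

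**Working it through.** There is no planned figure to reproduce, because no sample size, power or alpha value depends on this point. The check sets the required measurements (Table 11.1-1 footnote f, Sections 11.5 and 11.8) against what the definition needs (Table 26.2-1), by type of subject and using required data only.

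1. **CK normal, no new ischemic symptoms or signs.** The first element fails. Because the elements are joined by AND, the subject has no MI whatever the marker would have shown. This group is classifiable.
2. **CK normal, new ischemic symptoms or signs present.** The first element is met, so the biomarker element decides.
   - Troponin limb: no troponin is required, and nothing in the documents lets a normal CK stand in for it.
   - CK-MB limb: no CK-MB is required. Table 26.1-1 describes CK-MB as a fraction of CK, so reading a normal CK as negative is plausible here, but the protocol does not state that rule.
   - Result: not evaluable from required data.
3. **CK elevated after the procedure.** CK-MB or troponin must then be run, and either is enough for the threshold. If CK was normal at baseline, no baseline CK-MB or troponin is required, so the 50% rule may be uncheckable. If CK was elevated at both times, both values exist but may be of different markers.

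**When the 50% rule matters.** Let b be the baseline value and L the limit, both in multiples of the upper reference limit. A peak above L already implies a 50% rise unless 1.5 × b exceeds L. The rule therefore changes a classification only when b > L / 1.5:

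- troponin: 15 / 1.5 = 10 times the limit;
- CK-MB: 5 / 1.5 = 3.3 times the limit.

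The subjects at issue had a normal CK at baseline, and exclusion criterion EC2 removes acute MI within 30 days before the procedure. Baselines this high should be uncommon, so group 2 is the main gap.

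**Size.** The documents do not say how many subjects will have a normal CK together with ischemic symptoms or signs. Table 4.1-4 gives a periprocedural MI rate of 2.9% (7/243) in REPRISE II, but the protocol does not say which markers that study required. The figure cannot be treated as fully ascertained and then reduced by an assumed loss.

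**The case against.** The strongest defence is that the schedule is a minimum. Sites may run troponin or CK-MB at any time, and subjects with ischemic symptoms or signs are the ones in whom they would be expected to. Footnote t, Section 11.10 and Section 21.1 direct attention to the tests named in the definitions. Under Section 22.1.1 the CEC works from a dossier that may include source documents, and its charter, which is not among the documents, may hold a classification rule. Because CK-MB is a fraction of CK and is the preferred marker, screening on CK first is also a defensible choice for that limb.

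Much of this stands. It confines the problem mainly to the troponin limb in symptomatic subjects. It does not close the gap: none of those sections expressly overrides the CK condition, and a committee cannot adjudicate on an assay that was never run.

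Three stronger readings are tempting and are not supported.

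- *MI cannot be derived in any CK-normal subject.* The AND in the definition settles all those without ischemic symptoms or signs.
- *The MI rate is biased downward in a way that favours Lotus.* Equal under-ascertainment shrinks a difference in either direction and would help Lotus only if Lotus truly had more MI, which nothing here shows. Leaving the 50% rule unapplied for want of a baseline value would tend to over-count. There is no non-inferiority test on MI.
- *A stated share of events is lost.* No such share can be anchored in the documents.

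**Conclusion.** The mismatch between schedule and definition is real but narrow. In CK-normal subjects with new ischemic symptoms or signs, the biomarker element of periprocedural MI, especially its troponin limb, cannot be evaluated from the data the protocol requires, and the available text gives no rule for classifying them. A smaller gap affects the 50% rule when CK is normal at baseline and raised afterwards.

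Neither the size nor the direction of any bias between arms can be stated. The consequence is limited to a CEC-adjudicated additional measurement. MI is in neither primary composite (Sections 7.1.1 and 7.1.2), is not the secondary endpoint (Section 7.1.3), and is not in the VARC-2 30-day safety composite listed in Section 7.2.

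The conclusion assumes that some sites run only the required tests and that the CEC charter holds no rule for these subjects. This is a cheap improvement, not a threat to the trial's main conclusions.

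**What to change.** **For subjects still to be treated.** In Sections 11.5 and 11.8 and in footnote f of Table 11.1-1, require a marker named in the MI definition (CK-MB or troponin) regardless of total CK, with the same marker and assay at baseline and at both post-procedure draws. Total CK may be kept or dropped. One marker makes the criterion evaluable on that limb only, which is enough because the definition accepts either.

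**For subjects already treated.** Prespecify in the SAP or the CEC charter how CK-normal subjects without a CK-MB or troponin value are classified, and report by arm the number with an evaluable biomarker.

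**Cost.** The assay uses blood already drawn at three existing time points, so no visit or draw is added. The price is a slightly higher assay cost and possibly a less favourable reported MI rate. No power, alpha, primary or secondary analysis changes.
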